## Clinical Investigational Plan

### 4.2.1 Number of subjects required to be included in the study

Up to 40 subjects will be enrolled in this study. Of these, it is expected that 30 subjects will be successfully screened and complete the study. Patients who fail screening will not participate in the study.

### 4.2.2 Estimated time needed to enroll this subject population

Up to 40 subjects will be enrolled in this study. Of these, it is expected that 30 subjects will be successfully screened and complete the study. Patients who fail screening will not participate in the study.

## 4.3 OBJECTIVES

### 4.3.1 Primary Objective

To compare differences in therapeutic efficacy between conventional burst stimulation parameters (Burst train consisting of 5 pulses, Intraburst frequency: 500 Hz, Burst Rate: 40 Hz, Pulse width: 1000  $\mu$ s) and energy efficient burst microdosing stimulation paradigms listed below:

- Standard burst stimulation parameters with 5 seconds of STIM ON, followed by 5 seconds of STIM OFF
- Standard burst stimulation parameters with 5 seconds of STIM ON, followed by 10 seconds of STIM

### 4.3.2 Secondary Objective

To compare subjects' differences in quality of life, subjects' satisfaction, subjects' preference and incidence rate of adverse events between different stimulation paradigms.

## 4.4 ENDPOINTS

### 4.4.1 Primary Endpoint

Changes in Visual Analog Scale (VAS) scores between baseline and follow up visits

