### Clinical Investigational Plan

#### 1.0 SYNOPSIS

Title:	Burst Optimized Stimulation Study
Acronym:	BOSS
Purpose:	This purpose of this study is to evaluate the therapeutic efficacy of energy efficient burst microdosing stimulation paradigms in patients with chronic pain.
Primary Objectives:	To compare differences in therapeutic efficacy between conventional burst stimulation parameters (Burst train consisting of 5 pulses, Intraburst frequency: 500 Hz, Burst Rate: 40 Hz, Pulse width: 1000 μs) and energy efficient burst microdosing stimulation paradigms listed below: 
 
• Standard burst stimulation parameters with 5 seconds of STIM ON, followed by 5 seconds of STIM OFF
 
• Standard burst stimulation parameters with 5 seconds of STIM ON, followed by 10 seconds of STIM OFF
 

Secondary Objectives:	To compare differences in: 
 
• Quality of life
 
• Subject satisfaction
 
• Patient preference
 
• Incidence of adverse events
 
 
between standard burst stimulation and the two different burst microdosing paradigms.

Primary Endpoints:	
 
• Change in Visual Analog Scale (VAS) between baseline and follow up visits
 

Secondary Endpoints	Difference in 
 
• Quality of life (EQ-5D)
 
• Subject satisfaction
 
• Incidence rate of adverse events
 
 
between standard burst stimulation and the two different burst microdosing paradigms

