## Clinical Investigational Plan

### 6.2 PROCEDURES

The clinical study will be conducted in accordance with the CIP. All parties participating in the conduct of the clinical study will be qualified by education, training, or experience to perform their tasks and this training will be documented appropriately.

The clinical study will not commence until St. Jude Medical receives written approval from the EC and relevant regulatory authorities and all required documents have been collected from the site(s).

Table 1: List of all study specific activities/procedures

Study Activity	Visit	Screening	Follow up visit 1	Follow up visit 2	Follow up visit 3
Informed Consent		X			
Inclusion/Exclusion Criteria Screening		X			
Randomization		X			
Sequester patient programmer		X			
Return patient programmer					X
Provide pain diary		X	X	X	
Collect pain diary			X	X	X
VAS assessment			X	X	X
EQ-5D questionnaire			X	X	X
Subject satisfaction questionnaire			X	X	X
Collect programming parameter printouts			X	X	X
Stimulation reprogramming		X	X	X	
Document patient preference					X
Program preferred stimulation paradigm					X

Table 2: Visits Timeline

Visit	Screening	Follow up visit 1	Follow up visit 2	Follow up visit 3
Timing	At enrollment	14±5 days after screening visit	14±5 days after follow up visit 1	14±5 days after follow up visit 2

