### Clinical Investigational Plan

Enrollment activities must be performed before any other study procedure/visit. Enrollment information (name of the study, date of consent) should be recorded in the clinic records, and the Enrollment form should be completed and submitted in a timely manner (recommended within 5 days). Notification of enrollment to the sponsor will take place only when the sponsor receives the Enrollment form.

In case the subject was consented, but does not meet inclusion/exclusion criteria, the following actions will be taken:

If additional study procedures have not occurred:

- Document enrollment information (name of the study, date of consent) and inclusion/exclusion information in the clinic and/or study records; complete the Enrollment Form and all forms for the Screening visit. The forms must be authorized / approved by the principal or delegated investigator.
- The EC should be notified appropriately about any deviations with regards to obtaining the informed consent.

If additional study procedures have occurred:

- Document enrollment information (name of the study, date of consent) and inclusion/exclusion information in the clinic and/or study records; complete the Enrollment Form, all forms for the Screening visit, and the Withdrawal Forms. The forms must be authorized / approved by the principal or delegated investigator.
- Complete study deviation for inclusion/exclusion not met.
- The EC should be notified appropriately about any deviations with regards to obtaining the informed consent.

If the subject meets the inclusion/exclusion criteria, the patient programmer will be sequestered and the subjects will be provided a one-week pain diary. Subjects will be randomized to one of the three treatment groups and their stimulator will be programmed with the first stimulation paradigm according to the group assignment. Stimulation intensity will gradually be increased until the subject perceives the stimulation to find the Threshold for Perception (TP), and then the intensity will subsequently be reduced to the sub-perception level providing optimal pain relief. Subjects will then receive a one-week pain diary to assess the pain levels during the first assigned stimulation paradigm. One week after this visit, the subject will be contacted to schedule the first follow up visit and instructed to start recording pain levels on the pain diary.

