NOTE: As soon as the subject signs the Patient Informed Consent, adverse events need to be reported according to the guidelines mentioned in section 8.2.

The following activities and assessments will be performed during screening visit.

Timing of visit	Activities at visit	Case Report Form
Screening	
 
● Subject signs informed consent
 
● Subject is screened for inclusion/exclusion criteria
 
● Sequester Patient Programmer
 
● Provide pain diary
 
● Randomization
 
● Program IPG with first stimulation paradigm according to group assignment
 
	
 
● Enrollment Form
 
● Inclusion/Exclusion Form
 
● Randomization Parameters Form
 

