## Clinical Investigational Plan

### 6.4 FOLLOW UP VISIT 1

During the baseline visit, the investigator will collect the pain diary provided at the screening visit and record the current stimulation parameters in the parameters form. The subject will rate the pain during the first stimulation paradigm using the VAS, the EQ-5D and the satisfaction questionnaires administered by a clinician blinded to the stimulation paradigm. Subject’s stimulators will be programmed with the second stimulation paradigm according to the group assignment. Stimulation intensity will gradually be increased until the subject perceives the stimulation to find the Threshold for Perception (TP), and then the intensity will subsequently be reduced to the sub-perception level providing optimal pain relief. Subjects will be provided with a new pain diary for the assessment of the new stimulation paradigm. One week after this visit, the subject will be contacted to schedule the second follow up visit and instructed to start recording pain levels on the pain diary

The following activities and assessments will be performed during the first follow up visit.

Timing of visit	Activities at visit	Case Report Form
Follow up 1	
 
Collect pain diary
 
Programming parameters printout
 
Subject fills out pain assessment and quality of life questionnaires
 
Provide pain diary
 
Program IPG with second stimulation paradigm according to group assignment
 
	
 
VAS Form
 
EQ-5D Form
 
User Satisfaction Form
 
Parameters Form
 

### 6.5 FOLLOW UP VISIT 2

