### 12.0 STATISTICAL CONSIDERATIONS

#### 12.1 STATISTICAL DESIGN, HYPOTHESES, METHOD AND ANALYTICAL PROCEDURES

During baseline visit subjects will be randomized 1:1:1 to one of the three treatment sequences. An envelope-based system will be used for identifying which group the subject has been assigned. St. Jude Medical will provide sealed envelopes containing the site number and subject ID/sequence number. Inside the envelope, the randomization assignment will be identified along with the site number and subject ID/sequence number.

During reprogramming the subjects will not be made aware of what paradigm is currently being programmed. Pain questionnaires (VAS, EQ-5D, satisfaction and stimulation preference) will be administered by a clinician blinded to the currently programmed stimulation paradigm.

Scores from the subject's questionnaires as well as subject satisfaction will be compared between follow up visits using a repeated measure ANOVA under the hypothesis of equivalence between standard and burst microdosing stimulation paradigms.

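### The primary endpoint is VAS change from baseline, but the plan puts baseline at two different visits: one has no scheduled VAS, and the other is on-treatment with a paradigm that differs by sequence

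*Combined protocol and SAP*

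**What the plan says.** - **Endpoint.** Section 4.4.1 gives "Changes in Visual Analog Scale (VAS) scores between baseline and follow up visits". The Synopsis gives "Change in Visual Analog Scale (VAS) between baseline and follow up visits". Neither defines baseline.
- **Baseline as randomisation visit.** Section 12.1: "During baseline visit subjects will be randomized 1:1:1 to one of the three treatment sequences". Table 1 and Section 6.3 place randomisation at screening.
- **Baseline as follow-up 1.** Section 6.4, headed as follow-up visit 1, opens: "During the baseline visit, the investigator will collect the pain diary provided at the screening visit".
- **VAS schedule.** In Table 1 (Section 6.2) the row "VAS assessment" is marked at follow-up visits 1, 2 and 3, with nothing under Screening. The Section 6.3 activity list ends with "Program IPG with first stimulation paradigm according to group assignment". Its three forms cover enrollment, eligibility and randomization parameters; none is a VAS form.
- **Diary.** Section 6.3, after the first programming: "One week after this visit, the subject will be contacted to schedule the first follow up visit and instructed to start recording pain levels".
- **Analysis.** Section 12.1 says that questionnaire scores "will be compared between follow up visits using a repeated measure ANOVA under the hypothesis of equivalence between standard and burst microdosing stimulation paradigms". It mentions no baseline score and no change score.

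**The concern.** A change score needs one reference, measured in the same way for every subject. On one reading of this plan the reference is never collected. On the other it is a treatment outcome whose paradigm depends on the randomised sequence. The stated primary endpoint therefore either cannot be computed or means something different in each group, and it does not match the analysis in Section 12.1, which works without a baseline.

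Other text adds to the confusion. The Synopsis (Data Collection) describes follow-up 1 as an assessment of standard burst, and Section 6.5 describes follow-up 2 as an assessment of the first microdosing paradigm. Both are true of Group 1 only. The Synopsis (Design) describes a third follow-up visit and then refers to two.

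Section 12.2 says the study is meant to give early estimates of the effect size. It should be settled in advance which quantity is being estimated.

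**Working it through.** The plan gives no alpha, power, SD, margin or effect size, so there is no stated figure to reproduce. The check follows each reading through the schedule.

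**Inputs.** Allocation is 1:1:1 (Section 4.2) and 30 completers are expected (Section 12.2), so I assume 10 per sequence. Write S for standard burst, 5:5 and 5:10 for the microdosing paradigms (seconds on:off), and d1 and d2 for their true mean VAS differences from S. The sequences in Section 4.2 are:

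| Group | Follow-up 1 | Follow-up 2 | Follow-up 3 |
|---|---|---|---|
| 1 | S | 5:5 | 5:10 |
| 2 | 5:5 | 5:10 | S |
| 3 | 5:10 | S | 5:5 |

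**Reading A: baseline is screening.** Scheduled VAS scores are 3 per subject, 3 × 30 = 90 in all, and every one follows the first programming. Baseline scores: 0. The diary cannot stand in, because recording begins a week after the first paradigm is programmed.

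**Reading B: baseline is follow-up 1.** The reference is S in 10 subjects, 5:5 in 10 and 5:10 in 10, so 20 of 30 have a microdosing reference.

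**Effect on the paradigm contrasts** (complete data, independent errors of equal variance σ², no carryover, subject and paradigm fitted):

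- *All three end-of-period scores, 90 observations.* Each contrast with S is estimated without bias, with variance 2σ²/30 = 0.0667σ².
- *Changes from follow-up 1, at follow-ups 2 and 3 only, 60 observations.* With subject fitted, the reference cancels and the information left is follow-up 3 minus follow-up 2. Its expectation is d2 − d1 in Group 1, −d2 in Group 2 and d1 in Group 3. Each group mean has variance 2σ²/10 = 0.2σ². Least squares on these three means gives X′X = [[2, −1], [−1, 2]], whose inverse has diagonal 2/3. The variance of each contrast is 0.2σ² × 2/3 = 0.1333σ² (= 4σ²/30). The estimates are still unbiased.
- *Ratio.* 0.1333/0.0667 = 2.0; the standard error ratio is √2 = 1.41. A period term changes none of this, because period is orthogonal to paradigm in this layout.

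**A separate point on the Section 12.1 wording.** Taken literally, a comparison between visits sees the mean (0 + d1 + d2)/3 at every visit when sequences are balanced. Every visit contrast is then zero apart from period effects, whatever d1 and d2 are and whatever baseline is used.

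**The case against.** The strongest reply is that the baseline is not needed. Section 12.1 compares scores, its hypothesis names paradigms, and the three end-of-period scores needed to meet the objective in Section 4.3.1 are all scheduled. The trial is a feasibility study with no power claim. This stands, and it is why the point concerns the endpoint's definition and not the validity of the design.

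The doubled variance is also conditional: no section says that follow-up 1 would be used only as a subtracted reference. If all 90 scores are analysed, nothing is lost. A cruder calculation, averaging change scores by paradigm without fitting subject and leaving out the zero changes at follow-up 1, would give 1.5 times the true contrast: for 5:5 minus S, (2d1 − d2)/2 + (d1 + d2)/2 = 1.5d1. A repeated measures analysis would not do this, so I give it no weight.

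The reference to two follow-up visits in the Synopsis could mean that follow-up 1 is the baseline. The same paragraph has just described a third follow-up visit, so a miscount is the plainer reading. Either way the sentence has to change.

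Finally, Table 1 claims to list all activities but omits adverse event recording and the one-week contact, so an empty cell is not conclusive alone. The flow chart is not visible in the copy reviewed, and the case report forms are held separately. But the Section 6.3 activity list and its named forms agree with Table 1 that screening has no VAS. A VAS shown elsewhere would contradict both and would leave the two uses of baseline unresolved.

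**Conclusion.** The concern holds. As written, the primary endpoint has either no scheduled baseline score (0 of 30) or a reference that is standard burst in only about 10 of 30 completers. No bias in the paradigm contrasts is claimed. The possible loss is a doubling of variance, and only if follow-up 1 is used purely as a reference. The figures assume equal sequences, 30 completers with complete data, independent errors of equal variance and no carryover. The contradiction in the text needs none of these assumptions. It should be fixed, but it does not undermine the design.

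**What to change.** 1. Restate the primary endpoint in Section 4.4.1 and the Synopsis as the within-subject difference in end-of-period VAS, each microdosing paradigm minus standard burst. This matches the objective in Section 4.3.1 and the way Section 4.4.2 already frames the secondary endpoints. In Section 12.1, say that the repeated measures analysis compares paradigms, not visits: paradigm as the factor, subject in the model, period as an added term.
2. Use the word baseline for the screening visit only, which is where Section 12.1 puts it by tying it to randomisation. Correct the Synopsis (Design and Data Collection) and Sections 6.4 and 6.5 to match three sequences and three follow-up visits.
3. Only if a change-from-baseline summary is wanted: add VAS and EQ-5D to the Screening column of Table 1 and to Section 6.3, taken before the first reprogramming. The paradigm contrast does not depend on this.

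Items 1 and 2 need no new data or subjects. Item 3 adds one short questionnaire set, on forms already in use, at an existing visit. Because the declared primary endpoint changes, the amendment steps in Section 14.0 apply: a justification for each amended section, and notification to or approval by the ethics committee and authorities where required.

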### 4.4.2 Secondary Endpoint

Difference in:

- Quality of Life (EQ-5D)
- Subject satisfaction
- Subject preference
- Incidence rate of adverse events

between standard burst stimulation and the two burst microdosing paradigms.

## Clinical Investigational Plan

### 4.5 INCLUSION AND EXCLUSION CRITERIA

A subject, who meets all of the inclusion criteria, and none of the exclusion criteria, is eligible to participate in this study.

All subjects enrolled in the clinical study (including those withdrawn from the clinical study or lost to follow-up) will be accounted for and documented in an enrollment log, assigning an identification code linked to their names, alternative identification or contact information.

To participate in this clinical subject, the subject must meet all of the following inclusion criteria:

#### 4.5.1 Inclusion Criteria

- Subject has been implanted with a commercially available SJM spinal cord stimulator for control of chronic intractable back and/or leg pain
- Subject has been exclusively using burst stimulation for at least three months
- Subject is 18 years of age or older
- Subject's pain-related medication regimen was stable in the 4 weeks prior to the screening evaluation
- Subject agrees not to add or increase pain-related medication from activation through the 24 week follow-up visit
- Subject is willing to cooperate with the study requirements including compliance with the regimen and completion of all office visits

Subjects are not eligible for clinical study participation if they meet any of the following exclusion criteria:

#### 4.5.2 Exclusion Criteria

- Subject is currently participating in a clinical investigational study that includes an active treatment arm
- Subject is currently receiving, applying or considering seeking workers compensation, or is involved in disability litigation
- Subject has a non SJM neuromodulation device

## Clinical Investigational Plan

### 4.6 SUBJECT POPULATION

The study population will consist of patients with chronic pain for failed back surgery syndrome or neuropathic back and/or leg pain with an implanted commercially available SJM spinal cord stimulation device and have been using conventional burst stimulation parameters for the past three months as part of their clinical care.

#### 4.6.1 Subject Screening

Patients who are recommended by the Investigator as a candidate for the study will be fully informed about the study and asked to participate in the study. In case the patient agrees, a duly signed and dated Patient Informed Consent will be obtained. Subjects will then be screened by a member of the investigational team previously trained on the CIP and delegated to do so.

Subjects who do not meet the inclusion/exclusion criteria will not be eligible to participate in this study.

#### 4.6.2 Point of Enrollment

Subjects are considered enrolled in the study from the moment the subject has provided written Patient Informed Consent. (Refer to section 4.7 for the Informed Consent Process).

### 4.7 INFORMED CONSENT PROCESS

#### 4.7.1 General process

Prior to enrolling in the clinical study and conducting study-specific procedures, all subjects will be consented, as required by applicable regulations and the center's Ethic Committee (EC). Informed consent must be obtained from each subject prior to any study related procedures. The consent form must be signed and dated by the subject and by the person obtaining the consent.

The principal investigator or his/her authorized designee will conduct the Informed Consent Process. This process will include a verbal discussion with the subject on all aspects of the clinical study that are relevant to the subject's decision to participate in the clinical study.

The subject shall be provided with the informed consent form that is written in a language that is understandable to the subject and has been approved by the center's EC. Failure to obtain informed consent from a subject prior to study enrollment should be reported to St. Jude Medical within 5 working days and to the reviewing center's EC consistent with the center's EC reporting requirements.

## Clinical Investigational Plan

### 5.0 DEVICE UNDER INVESTIGATION AND CONTROL/COMPARATORS (IF APPLICABLE)

#### 5.1 DEVICE DESCRIPTION

Subjects with SJM commercially available spinal cord stimulation devices capable of delivering burst stimulation will be considered for participation in this study

The spinal cord stimulator system consists of the following components:

- Implantable Pulse Generator (IPG) - a software controlled, battery powered stimulator that generates the electrical pulses
- Lead - sterile stimulating electrode that is placed in the epidural space of the spinal cord
- Extensions - The IPG connects to the implanted extensions, which in turn connects to the leads
- IPG Charger - External power source that allows for recharging of the IPG internal battery (only for rechargeable IPG models)
- Clinician Programmer - Electronic device that communicates wirelessly with the IPG and allow the clinician to alter stimulation parameters and program different stimulation patterns

The device components used in the study should be manufactured by St Jude Medical Inc, commercially available, and should already be part of the pain management continuum of the subjects before study enrollment (i.e. the study will be performed on subjects that already have an implanted SCS system). Any SJM commercially available IPG capable of delivering burst stimulation, SCS lead and extension can be used in this study.

Further description of each component of a SCS system to be used in this study can be found below.

